4.1 Study Objectives

The **overall objective** of this study is to reduce the burden of COVID-19 by expanding the reach of inpatient palliative care services, especially for patients with ADRD/Delirium. We propose to conduct a stepped wedge cluster randomized trial (SW-CRT) of a PCE video intervention among hospitalized patients aged 65 and over, or any patient ≥ 18 years with ADRD/Delirium and their caregivers in the ward and ICU settings of two major hospitals: Boston Medical Center (BMC) and North Shore University Hospital. Patient outcomes will be abstracted from electronic health records with Natural Language Processing (NLP).

We will test our hypotheses via the following **Specific Aims**:

Aim 1: To test the effects of a PCE video intervention leveraging video decision aids on the quality of end-of-life care. We will conduct a SW-CRT to evaluate intervention effectiveness by comparing the following outcomes among 9,000 hospitalized patients: ACP documentation; preferences for resuscitation; palliative care consults; and, hospice use. **Hypotheses:** *A higher proportion of patients in the intervention phase (vs. control) will: (1) complete advance care plans (primary outcome), (2) have documented resuscitation preferences, (3) have palliative care consults, (4) enroll in hospice over the course of one year of follow-up, and (5) have documented health care proxies.*

Aim 2a: The manual chart review activity is intended only for the patients whose caregiver participated in the survey activity. It is distinctive from the NLP activities described in our protocol which identify ACP documentation from the free-text of clinical notes. The chart review will involve a thorough human review of structured ACP elements such as DNR/DNI order, MOLST/POLST and Health Care Proxy form completion in each patient's chart.

Aim 2b: To characterize caregiver-centered outcomes of patients with ADRD/Delirium, including: (1) knowledge, (2) confidence in future care, (3) communication satisfaction, (4) decisional satisfaction, and (5) decisional conflict in 600 caregivers of patients with ADRD/Delirium admitted to the hospital. **Hypothesis:** *Intervention phase caregivers of patients with ADRD/Delirium (vs. control) will have higher knowledge, confidence, communication satisfaction, decisional satisfaction, and lower decisional conflict.*

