Every 2 months (the size of each step; 1 baseline + 7 steps = 8 data transfers) the outcomes of interest using NLP will be transferred to our data collection site (DFCI). Data on the following outcomes will be collected until the end of the study period.

- ACP discussion (e.g., goals-of-care discussion, advance directive, MOLST/POLST, code status, etc.)
- Resuscitation preferences
- Palliative care consults
- Hospice Use
- Health care proxy discussion

As stated above, direct identifiers will be held at each respective site (BMC researchers can see BMC identifiers but not North Shore University Hospital's identifiers, and vice versa.) The risks will be minimal as the data will be stored and analyzed on a HIPAA secure cluster at each site. None of the data will be stored in paper form. The data and identifiers will be kept for seven years after the end of the study period on the HIPAA secure cluster computer at each site. After the seven years, all HIPAA identifiers and all linking codes will be permanently destroyed in accordance with regulation.

NLP Validation

Prior to the use of NLP for outcome assessment in this trial, we will entrain and validate the NLP process for each of our two study sites. Specifically, we will use historic note data from a sample of 20 patients from each site who meet enrollment criteria. We will then measure the validity of this process by comparing results from human assisted NLP to a human chart review. The goal of the keyword library validation process is to ensure that the keyword library and abstraction guidelines accurately represent the language used to communicate information associated study outcomes. The semi-automated note annotation process will be cross-validated across both sites. Clinical notes will be the substrate of this process and must be requested from each site's clinical data warehouse.

Each site will ensure that the appropriate IRB and Data Sharing protocols are in place before this activity begins.

Chart Review

EHR data will be extracted by manual chart review on all Aim 2a patients whose caregiver completes a survey (2b). This survey will be limited to the inpatient stay that generated the survey, and include the following elements for collection of secondary outcomes:

- DNR/DNI order
- MOLST/POLST filed
- Resuscitation/Intubation preferences
- Health Care Proxy specified
- Palliative Care Consult during hospitalization

- Discharge Disposition

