A detailed chart review instrument is attached to the protocol.

Withdrawal

We do not anticipate any circumstances where the caregiver will withdraw from participation in the study. Study staff will make clear to the caregiver that participation is entirely voluntary and may be withdrawn at any time.

Masking

Due to the nature of the intervention, participants and staff will not be blinded to the intervention.

The NLP outcomes adjudication process is not fully automated in this study. We are doing a human-assisted NLP process in which a staff member validates the text presented in the software as a possible outcome. For NLP analysis, the following steps will be taken to ensure blinding to study step assignment by the staff member doing the NLP outcome attribution:

- Prior to adjudication activities, names will be coded
- Annotation will be performed in large batches with all patients enrolled who have clinical notes to that point.
- NLP notes for adjudication will not be grouped by Study ID when presented to annotators. Each note will be annotated individually, without reference to concepts contained in other notes annotated before or after.
- When possible, a staff member who did not enroll the participants will perform the annotation.

Caregiver Surveys

Caregivers will be surveyed using a REDcap survey. The REDCap project will be hosted by BUMC, both sites will enter data into the same project. All subjects will be assigned a unique identifier that will be entered into REDCap. All other PHI will be retained in a linking file that is not shared outside the institution.

Caregiver data will be linked with the associated patient EHR data, but this linking file will be kept locally, and only HIPAA LDS will be shared with other sites included on this protocol.

Costs/Payment

There are no costs to subjects for participating in this study.

Caregivers will be compensated \$50 for completing the survey.

10 Assessment of Safety and Data Safety Monitoring Plan (DSMP)

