distributions of the uncertainty and knowledge scale scores, the outcomes of interest between intervention and usual care subjects, as well as the distributional characteristics of all other salient study variables. We will generate descriptive statistics (means, standard deviations, quantiles for continuous variables; counts and percentages for categorical variables) and schematic plots (box-and-whisker, quantile-quantile plots). Given the nature of the cluster randomization that we will employ, we will utilize statistical analytic methods that take the correlated nature of the data into account as well as the influence of time to account for secular trends. In this study, we will examine both the health system and hospital unit as clustering variables, with the hospital unit as the primary clustering variable. We will compare the intervention and usual care groups on salient variables in order to assess balance in the distributions of these variables. Variables found to differ between the study groups will be further evaluated to assess their confounding effects of intervention vs. usual care differences on outcomes in multivariable analyses for correlated (clustered) data.

Aim 1. To test the combined effects of a COVID-19 ACP Educator-led, video-assisted palliative care intervention on rates of: ACP documentation; Medical orders for resuscitation preferences in the EHR; Palliative Care Consults; and, Hospice use. ***Hypothesis: A higher proportion of patients in the intervention phase (vs. control) will: complete ACP documentation (primary trial outcome), have documented orders for resuscitation preferences, have palliative care consults, and enroll in hospice.***

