We will conduct analyses related to potential effect modification as a step in our model validation process and to identify relationships that can be examined more fully in future research. Should interactions not be found to be statistically significant, we will fit a main effects-only model and use it to formally evaluate confounding by applying a change-in-estimates approach, with a 10% change in estimates being an initial screening criterion. **Secondary outcomes:** Similar procedures will be undertaken to assess intervention effects for the other EHR derived outcomes (documented orders for resuscitation preferences, palliative care consults, hospice enrollment, and documented health care proxies).

For our primary analysis, we will consider our primary outcome (ACP documentation) and our secondary outcomes (resuscitation preferences, palliative care, hospice use, and health care proxies) only for the patient's index hospitalization. However, because we expect some patients to have multiple rehospitalizations during the same step and may also include intervention time (i.e., crossover design), we will perform secondary analyses on all of our primary and secondary outcomes for each patient reviewing all EHR records from the index hospitalization of the patient until their death (or through study period). We will also perform stratified sensitivity analyses of patients who contribute only to control period vs. patients who contribute only to intervention period vs. those that contribute to both control and intervention periods.

We will conduct the above analyses on all Aim 1 and Aim 2a patients for the study primary and secondary outcomes.

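### Aim 1 tests documented health care proxies but collects proxy discussions, and the resuscitation, consult and hospice outcomes have no stated rule separating talk in a note from the event

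*Combined protocol and SAP*

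**What the plan says.** Section 12.3 gives the EHR-derived secondary outcomes for Aim 1 as "documented orders for resuscitation preferences, palliative care consults, hospice enrollment, and documented health care proxies". Its restatement of Aim 1 has "Medical orders for resuscitation preferences in the EHR". Sections 4.1 and 12.1 instead hypothesise documented preferences for resuscitation, and Section 4.2.2 lists code status preferences.

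On collection, Section 9 (NLP Data Collection) says that every two months "the outcomes of interest using NLP will be transferred to our data collection site (DFCI"). It lists five items: ACP discussion, resuscitation preferences, palliative care consults, hospice use, and "Health care proxy discussion". Section 9 (NLP Validation) makes clinical notes the material that the process reads. Section 9 (Masking) adds that a staff member validates flagged text and that "Each note will be annotated individually, without reference to concepts contained in other notes annotated before or after".

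Structured elements (DNR/DNI order, MOLST/POLST, proxy form) belong to a manual chart review. Section 4.1 says of that review: "It is distinctive from the NLP activities described in our protocol which identify ACP documentation from the free-text of clinical notes". It is limited to patients whose caregiver was surveyed, with a target of 600.

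Under Sections 5 and 8 the educator discusses goals of care, can show CPR and hospice videos, recommends consults to the treating team, and completes ACP documentation in the EHR. Section 9 (Recruitment) gives control-phase units usual care without the educator.

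**The concern.** Several secondary outcomes are named as things that happened: an order, an enrolment, a proxy on record. The data described for nearly all Aim 1 patients are note text. The protocol itself separates the two sources and keeps the structured one for a small subset.

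This matters more than usual because the intervention consists of conversation and documentation on these same topics. If talk is counted as the event, the extra text sits mainly in the intervention phase. The trial could then report more proxies or consults when what rose was discussion of them. Blinding the annotators does not remove this, since the text they read is itself produced by the intervention.

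**Working it through.** The plan gives no rates or power figures for the secondary outcomes, so there is no figure of its own to reproduce. The first check sets the sections side by side.

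| Outcome | Tested (12.3) | Hypothesis (4.1, 12.1) | NLP item (Section 9) | Reading |
|---|---|---|---|---|
| Proxy | documented proxy | documented proxy | proxy discussion | Direct conflict |
| Resuscitation | orders, and in one paragraph preferences | documented preferences | preferences | Inconsistent naming |
| Consult | consult | consult | consult | Named as an event; no visible rule for a recommendation |
| Hospice | enrolment, index stay in the main analysis | enrolment over one year | hospice use | Named as an event; no visible rule for a discussion; windows differ |

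**Share with structured review.** 600 / 15,000 = 4.0%, using the Aim 1 total in Sections 7.1, 9, 12.1 and 12.2. With the 9,000 in Section 4.1 it is 600 / 9,000 = 6.7%. Both treat the chart-review patients as a subset of Aim 1. Aim 2a admits patients from age 18, so the share could be smaller.

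**What a phase difference in error would do (illustration).** Let p be the true event rate, equal in both phases, and let m1 and m0 be the shares of non-events scored as events in the intervention and control phases. If every true event is detected, the apparent rate is p + (1 − p)m, and the false difference is (1 − p)(m1 − m0). It is zero if m1 = m0. All these inputs are assumptions.

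- p = 10%, m1 = 2%, m0 = 0: 0.90 × 0.02 = 1.8 points.
- p = 10%, m1 = 5%, m0 = 0: 0.90 × 0.05 = 4.5 points.

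To judge whether such differences would reach significance, I took 15,000 records split equally and divided by a design effect. The plan's value is 2.72. With its ICC of 0.01, k = 7 steps, one baseline period, and n = 15,000 / (7 × 8) = 267.9 per cluster-period, the usual stepped-wedge formula gives

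[1 + 0.01(7n + n − 1)] / [1 + 0.01(7n/2 + n − 1)] × 3(0.99)(8) / [2(7 − 1/7)] = (22.42 / 13.04) × 1.7325 = 2.98.

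The effective size per group is then 15,000 / 2.72 / 2 = 2,757 or 15,000 / 2.98 / 2 = 2,517. Under a two-sided 0.05 test with no true effect, 10.0% vs 11.8% is significant with probability 54% to 57%, and 10.0% vs 14.5% with probability above 99%.

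**What the planned validation can exclude.** It uses historic notes from 20 patients per site. Even with no false positives, and taking all 20 as non-events with one decision each, the one-sided 95% upper limit is 1 − 0.05^(1/20) = 13.9% for a site, and 1 − 0.05^(1/40) = 7.2% for both together. Historic notes would also contain none written by this trial's educators.

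**The case against.** A reader might infer that all four secondary outcomes are measured as bare mentions and that four of the five Aim 1 hypotheses are therefore biased. The documents do not support that.

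- Only the proxy item is called a discussion. Consults and hospice use are listed as events.
- A preference recorded in a note meets the resuscitation outcome as Sections 4.1, 4.2.2 and 12.1 define it. It is a false positive only against the word *orders* in Section 12.3.
- A person confirms the flagged text under abstraction guidelines that are not reproduced. Those may already score a recommended consult as negative, in which case annotating notes singly does no harm.
- Sections 12.3 and 11.5 speak of EHR data generally, so a structured extract for Aim 1 is not ruled out.
- Clinicians in usual care also write about code status, hospice and proxies, so m0 is unlikely to be zero.

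All of this stands, and it limits the point for three of the outcomes. It does not resolve the proxy conflict, where the item collected differs by name from the item tested. Nor does it supply the missing rule for consults and hospice, or a described structured source for Aim 1.

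**Conclusion.** The point holds in limited form. For proxies, the plan as written would report discussions as documented proxies. For resuscitation, orders and preferences are used interchangeably. For consults and hospice, the gap is an unstated rule, not a demonstrated error. Because the educator generates relevant text only in the intervention phase, any counting of talk as the event may be more frequent there and may favour the intervention. The direction is plausible, not proven.

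The size is unknown. The 1.8 and 4.5 points rest on an assumed 10% true rate, assumed miscounting of 2% and 5%, no control-phase miscounting and full detection of true events. They show only that, at 15,000 records, a small phase difference in error could matter. For proxies, if the tested variable is simply renamed a discussion, it is measured correctly and the misclassification disappears.

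A reader might extend this to the primary outcome. That would be wrong: Section 4.2.1 defines it as qualifying documentation in the EHR note, which is what the NLP process reads.

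**What to change.** 1. For all Aim 1 patients, add structured fields to the two-monthly extraction in Section 11.5: proxy named or form on file, DNR/DNI order or MOLST/POLST, and completed palliative care consult. State that a default full-code order does not count as a documented preference. Report the NLP results as separately named documented-discussion outcomes. Where a site lacks a field, rename that outcome as a discussion and remove *orders* or *documented health care proxies* from its hypothesis.
2. For hospice, use discharge disposition to hospice for the index-stay analysis only. It cannot measure enrolment over one year, so reconcile it with the hypothesis in Sections 4.1 and 12.1.
3. Use the planned chart review of about 600 patients to estimate NLP false-positive and false-negative rates for proxy, resuscitation and consult, separately by phase. With 300 per phase and an assumed 10% event rate there are 270 non-events. A false-positive rate of 5% would then have a 95% margin of 1.96 × √(0.05 × 0.95 / 270) = 2.6 points, ignoring clustering. These patients all have ADRD or delirium, and Section 7.1 draws some controls from nine added units, so the rates may not carry over fully to Aim 1.

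The cost is field mapping at two sites and an amendment to the wording. Structured event rates may be lower than note-based rates. The chart review is already planned, so step 3 needs only linkage and analysis.

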Population:	
Aim 1: Patients ≥ 65 years admitted to one of the study inpatient units
 
Aim 2a: Any patient ≥ 18 years admitted to one of the study inpatient units with ADRD/delirium
 
Aim 2b: Adult Caregiver of any patient in aim 2a

Intervention:	Palliative Care Educator using video decision aid shown at time of admission to patients/caregivers in wards/units randomized to the intervention phase
Objectives:	The overall objective of the present proposal is to reduce the burden of COVID-19 and advanced illness and its consequences for an aging U.S. population.
Design/Methodology:	This project is a multi-center stepped wedge cluster randomized trial of an advance care planning (ACP) video intervention (vs. standard of care) using a Palliative Care Educator among patients ≥ 65 years OR any patient ≥ 18 years old with ADRD regardless of age admitted to one of the study inpatient units
Total Study Duration:	2 years
Subject Participation Duration:	EHR data collection during the 16 months of enrollment (2 months baseline plus 14 months intervention steps). EHR data abstracted for one year after the end of the 16 months of enrollment.

3 Background/Rationale & Purpose

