4.2.2 Secondary Outcome Measures

Secondary outcomes include:

- Code status preferences (Aim 1)
- Use of palliative care consult/services (Aim 1)
- Hospice use (Aim 1)
- Health Care Proxy (Aim 1)

Secondary outcomes related to Aim 2a (patients 18+ years admitted to one of the study inpatient units with ADRD/delirium) include:

- Documentation of ACP Preferences in Electronic Health Record

Secondary outcomes related to Aim 2b (caregivers of patients with ADRD/Delirium) include:

- ACP knowledge (Aim 2)
- Confidence in future care (Aim 2)
- Communication satisfaction (Aim 2)
- Decisional satisfaction (Aim 2)
- Decisional conflict (Aim 2)

5 Study Design

This is pragmatic SW-CRT of a PCE-led, video-assisted COVID-19 ACP intervention in inpatient-based units (3 medical-surgical wards, Medical ICU, Cardiac ICU, Neurology ICU, step-down unit) at two hospitals: BMC and North Shore University Hospital (Northwell Health). All inpatients ≥ 65 and all patients with ADRD/Delirium ≥ 18 who are hospitalized on a unit during the intervention phase will receive the intervention.

This 2-year study (2 month data collection and tool preparation, staff training and site standardization (we are already embedded in both health systems doing similar work; thus this

short timeframe is feasible); 16 months rolling recruitment and surveying; 2 months data cleaning and analysis, and 4 months manuscript preparation and dissemination of findings) will roll out the intervention to 14 randomized inpatient units at 2 sites. Every two months, an additional inpatient unit will be added to our intervention at each hospital, i.e., there will be seven waves or "steps"; for a total of 7 units at each hospital.

Consistent with a SW-CRT with two hospital units per step (cluster), prior to the collection of any data in the pre-intervention period, we will generate a set of uniform random numbers for each of the seven clusters to be assigned to a starting period for the study intervention. There will be eight study periods in total with a usual care period at the start of the study for all clusters. The first randomized intervention period will then begin in period two.

Cluster	Baseline	14 Months of Clustered Intervention Expansion							
	M0	M2	M4	M6	M8	M10	M12	M14	
1									
2									
3									
4									
5									
6									
7									

The data needed to assess the outcomes for all patients will be derived from each hospital's EHR (Aim 1).

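### The secondary follow-up analysis has no common window and no settled end date, so later exposure of control-phase patients can dilute its estimate

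*Combined protocol and SAP*

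**What the plan says.** Section 12.3 takes the primary and secondary outcomes in the primary analysis "only for the patient's index hospitalization". Because rehospitalizations are expected, it then adds secondary analyses of all these outcomes, "reviewing all EHR records from the index hospitalization of the patient until their death (or through study period". No window length is given.

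The end of that period is not consistent across the documents:

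- The synopsis (participation duration) has "EHR data collection during the 16 months of enrollment (2 months baseline plus 14 months intervention steps"), followed by "EHR data abstracted for one year after the end of the 16 months of enrollment". That is month 28 from the start of enrollment. The same table gives a total study duration of 2 years.
- Section 5 divides the two years into 2 + 16 + 2 + 4 = 24 months and leaves no room for a further year of records.
- Section 9 (NLP data collection) plans eight two-monthly transfers, which implies about month 16, and otherwise refers only to the end of the study.

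On the design, Section 5 says: "There will be eight study periods in total with a usual care period at the start of the study for all clusters". Random numbers are drawn "for each of the seven clusters to be assigned to a starting period for the study intervention", and "Every two months, an additional inpatient unit will be added to our intervention at each hospital".

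Section 12.3 also commits to intent-to-treat, to modelling time trends, and to strata of patients who contribute to control only, intervention only, or both. It foresees that patients may later have intervention time. It does not say to which phase an outcome after that point belongs. Sections 4.1 and 12.1 hypothesise more hospice enrollment within one year of follow-up.

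**The concern.** In a stepped wedge, control-phase patients enter early and intervention-phase patients late. A window that closes on one calendar date therefore gives the two phases different time at risk for yes/no outcomes that accumulate. It also runs past the date on which each control-phase patient's own unit starts the intervention, so a patient whose index stay was under usual care can be readmitted and documented by the Palliative Care Educator (PCE).

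Two things are at stake. Crude follow-up proportions will look too favourable to control. And if patients keep their index phase, the adjusted effect is pulled toward no effect. This matters most for hospice: the primary analysis limits it to the index stay, so the open-ended analysis is the only planned one that could address the one-year hypothesis, and it does not use one year.

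**Working it through.** **Inputs.** 7 clusters (2 units each), 8 two-month periods (Section 5), 16 months of enrollment (synopsis). Check: 8 × 2 = 16, which agrees. Assumptions: equal admissions per cluster-period, entry at mid-period, no deaths. Cluster c is in control for periods 1 to c and switches at month 2c.

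**Entry dates.** There are 28 control and 28 intervention cells.

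- Control, sum of periods: 1+3+6+10+15+21+28 = 84, mean 84/28 = 3.
- Intervention: 7 × 36 − 84 = 168, mean 168/28 = 6.
- Mean entry month = 2 × period − 1: 5 for control, 11 for intervention.

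**Potential follow-up.**

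| Data end | Control | Intervention | Gap |
|---|---|---|---|
| Month 16 | 16 − 5 = 11 | 16 − 11 = 5 | 6 |
| Month 28 | 28 − 5 = 23 | 28 − 11 = 17 | 6 |

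**Effect of length alone.** Assume no intervention effect and a constant hazard of 1% per month to month 16. The expected proportions are 10.36% (control) and 4.82% (intervention), a crude odds ratio of (0.0482/0.9518)/(0.1036/0.8964) = 0.44. Over hazards of 0.5% to 4% per month, the crude odds ratio is 0.39–0.45 (month 16) or 0.64–0.73 (month 28). With period in the model, linear or categorical, it returns to 1.00, because patients indexed in the same period have the same potential follow-up in either phase.

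**Crossover.** The mean switch month over control cells is 2 × (sum of c²)/28 = 2 × 140/28 = 10.

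- Month 16: (16 − 10)/11 = 6/11 = 55% of control person-time follows the switch.
- Month 28: (28 − 10)/23 = 18/23 = 78%.

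**What crossover does to an adjusted estimate.** The documents give no readmission rate, so I assume r = 1% to 5% per month, readmission to the index unit, and per-admission documentation of 25% under control and 35% under intervention (the Section 12.2 rates). With entry month m, switch month s and data end E, the probability of no documentation is:

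- intervention: 0.65 × exp[−0.35r(E − m)]
- control: 0.75 × exp{−r[0.25(s − m) + 0.35(E − s)]}

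Logistic fits to these expected values, with period and cluster as factors, give these odds ratios:

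| r per month | No crossover, month 16 / 28 | Open window, month 16 | Open window, month 28 | 60 days |
|---|---|---|---|---|
| 1% | 1.616 / 1.618 | 1.570 | 1.513 | 1.611 |
| 3% | 1.620 / 1.636 | 1.502 | 1.395 | 1.604 |
| 5% | 1.626 / 1.662 | 1.452 | 1.330 | 1.597 |

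As an outer limit, suppose every patient has a 1.5-fold hazard as soon as the index unit switches (base hazard 1% or 2% per month). The adjusted odds ratio then falls from 1.53–1.67 to 1.00–1.01.

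**Fixed windows.** A control cell entered d periods before the last control period has 1 + 2d months to its switch. For d = 0 to 6 there are 7, 6, 5, 4, 3, 2 and 1 such cells.

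- 60 days (one step, 2 months): only d = 0 is affected, so 7 × 1/(28 × 2) = 12.5% of control time.
- 365 days: (7×11 + 6×9 + 5×7 + 4×5 + 3×3 + 2×1 + 0)/(28 × 12) = 197/336 = 59%.
- Both windows are complete for everyone only if the data run long enough. At month 16, 60 days gives 2.0 against (21×2 + 7×1)/28 = 1.75 months, and 365 days gives 10.0 against 5.0. At month 28, 365 days gives 12.0 against 12.0.

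**The nine control-only units (Section 7.1).** If they contribute equally to Aim 1, starting in period 1, the mean control period is (168 + 324)/(56 + 72) = 3.84 and the gap is 4.3 months. The post-switch share is 336/1192 = 28% (month 16) or 1008/2728 = 37% (month 28). Starting in period 5, the mean is (168 + 234)/(56 + 36) = 4.37 and the gap 3.3 months. The shares are 336/760 = 44% and 1008/1864 = 54%.

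**The case against.** The case for leaving the plan alone has four parts.

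1. **The primary analysis is not touched.** This stands in full: every outcome is analysed first on the index stay alone.
2. **The length gap is already handled.** A reader might infer that six extra months of control follow-up bias the modelled effect. The documents do not support that, because Section 12.3 commits to modelling time and applies similar procedures to the secondary outcomes. What remains is that the form of the time term is unstated and that crude proportions stay distorted.
3. **The plan does not say that outcomes after crossover count as control.** A reader might take this as stated. It is only the natural reading of intent-to-treat. The eight-hour rule in Section 12.3 covers unit moves within the index stay, not later admissions, so attribution is open.
4. **Crossover was foreseen, and the shares overstate it.** The plan names later intervention time and stratifies on it. But the both-phases stratum requires a patient to survive and be readmitted, so the strata are defined after index and are not randomized comparisons. They describe crossover and do not correct it. The 55% and 78% are indeed upper bounds on exposure through the index unit: only readmitted patients can be exposed, and the shares fall if the nine control-only units enter Aim 1, which Section 7.1 leaves unclear.

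**Conclusion.** The point holds for the secondary follow-up analysis only. That analysis has no common window, no settled end date and no rule for outcomes after crossover. The six-month gap in potential follow-up follows exactly from the schedule under equal cell sizes and no deaths. It affects crude proportions and is largely absorbed by an adequate period term.

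Crossover is what survives adjustment. Under analysis by index phase and assumed readmission of 1–5% per month, the odds ratio moves from about 1.6 to 1.45–1.57 with data to month 16, or to 1.33–1.51 with data to month 28. The direction, toward no effect, does not depend on the assumed rate as long as the intervention raises documentation; the size does. The choice between month 16 and month 28 alone changes the result, which is reason enough to fix it before analysis. A reader might go further and conclude that the trial's main result is at risk; the restriction to the index stay rules that out.

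**What to change.** In Section 12.3, replace the open-ended window with fixed windows from index admission, the same for every patient, and state that patients are analysed by phase at index with categorical period effects.

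- **Hospice: 365 days**, to match the hypothesis in Sections 4.1 and 12.1, with records to month 28 for all patients as the synopsis allows. Reconcile that date with the two-year total, the Section 5 timeline and the eight transfers in Section 9.
- **All outcomes: a short window**, for example one step (60 days), as the analysis least affected by crossover. It too needs records beyond month 16 to be complete for the last period.
- **Report** the share of control-index patients with a later intervention-phase admission, and say whether the nine control-only units enter Aim 1. Keep the three strata as description only.

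The cost is SAP wording and a date cut in programming, plus abstraction to month 28 if the shorter timeline was the one intended. The short window counts fewer late events. The 365-day result stays diluted, with about 59% of control time after the index unit's switch on the 14-unit grid, and should be reported as such.
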